6.7. Treatment Compliance

Treatment compliance with investigational product will be summarized for subjects who enter the Induction and Maintenance Periods. Treatment compliance for each subject will be calculated as:

$$\text{Treatment compliance (\%)} = 100 \times \frac{\text{Total number of injections administered}}{\text{Total number of injections prescribed}}$$

- The number of injections prescribed can be derived from the IWRS study drug dispense dataset.
- The total number of injections administered will be derived using the response to the question “Was dose administered?” on the Exposure eCRF page.

A subject will be considered significantly noncompliant if he or she fails to attend for administration of study medication within the required treatment window as defined in the protocol schedule of activities. Overall compliance with therapy is defined to be missing no more than 20% of the expected doses and not missing 2 consecutive doses. Proportions of subjects who demonstrate overall compliance during the Induction Period will be compared between treatment groups using Fisher’s exact test.

Subject treatment compliance will be summarized for the ITT and Maintenance populations. A by-subject listing of study treatment administration and compliance for the ITT and Maintenance populations will be provided.

6.8. Concomitant Therapy

Medications will be classified into anatomical therapeutic chemical (ATC) drug classes using the latest version of the World Health Organization (WHO) drug dictionary.

Medication start and stop dates will be compared to the date of first dose of treatment in each treatment period to allow medications to be classified as Concomitant for each treatment period.

Prior medications are those medications that start and stop prior to the date of first dose of study treatment. Concomitant medications are those medications that start before, on or after the first day of study treatment of the defined treatment period and continue into the treatment period. Concomitant medications are assigned to the treatment period in which they are actually ongoing. For example, if a patient is receiving concomitant medication during the Induction Period but has a stop date during the Induction Period, the same medication would not be listed as a concomitant medication during the latter periods unless patient has a new start date.

Prior therapy (reported before randomization) and current concomitant therapy (reported after randomization) will be presented separately in frequency tables by drug name for all randomized patients.

The medical monitor for this study will identify the corticosteroids used by the patients from the list of concomitant medication collected during the course of this study. A summary table for the number and percent of patients using corticosteroids during the Induction Period will be presented by the treatment groups. This table will also include a summary on the quantity of corticosteroid used by the patients, if an imbalance is observed between dosing groups. Corticosteroid use may also be summarized in conjunction with efficacy.

6.9. Efficacy Analyses

[Table 6.2](#) includes the description and derivation of the efficacy/health outcomes measures and endpoints.

[Table 6.3](#) provides the detailed analyses including analysis type, method and imputation, population, time point, and dosing regimen comparisons for efficacy/health outcomes analyses.

Table 6.2. Description and Derivation of Efficacy/Health Outcomes Measures and Endpoints

Measure	Description	Variable	Derivation / Comment	Imputation Approach if with Missing Components
PASI	
Psoriasis Area and Severity Index (PASI): combines assessments of the extent of body-surface involvement in 4 anatomical regions (head and neck, trunk, arms, and legs) and the severity of scaling (S), redness (R), and plaque induration/infiltration (thickness, T) in each region, yielding an overall score of 0 for no psoriasis to 72 for the most severe disease (Fredriksson and Pettersson 1978). Severity is rated for each index (R, S, T) on a 0-4 scale (0 for no involvement up to 4 for very severe involvement):
 
 0 = none 1 = slight 2 = moderate 3 = severe 4 = very severe 
The body is divided into 4 anatomical regions comprising the head (h), upper limb (u), trunk (t), and lower limb (l). In each of these areas, the fraction of total body surface area affected is graded on a 0-6 scale (0 for no involvement; up to 6 for 90% - 100% involvement):
 
 0 = 0% (clear) 1 = >0% to <10% 2 = 10% to <30% 3 = 30% to <50% 4 = 50% to <70% 5 = 70% to <90% 6 = 90% to 100% 	PASI score	
The composite PASI score is calculated by multiplying the sum of the individual-severity scores for each area by the weighted area-of-involvement score for that respective area, and then summing the 4 resulting quantities as follows: $PASI = 0.1(R_h + T_h + S_h)A_h + 0.2(R_u + T_u + S_u)A_u + 0.3(R_t + T_t + S_t)A_t + 0.4(R_l + T_l + S_l)A_l$ Where, R_h, R_u, R_t, R_l = redness score of plaques on the head, upper limb, trunk, and lower limb, scored 0-4 respectively; T_h, T_u, T_t, T_l = thickness score of plaques on the head, upper limb, trunk, and lower limb, scored 0-4 respectively; S_h, S_u, S_t, S_l = scaliness score of plaques on the head, upper limb, trunk, and lower limb, scored 0-4 respectively; A_h, A_u, A_t, A_l = numerical value translation of % area of psoriatic involvement score for the head, upper limb, trunk, and lower limb, respectively. PASI scores are treated as a continuous score, with 0.1 increments within these values.
	If any individual score is missing, the PASI score will not be calculated, hence missing
		PASI change from baseline	Calculated as: observed PASI – baseline PASI	Missing if baseline or observed value is missing
		PASI percent improvement from baseline	Calculated as: $Percent\ improvement\ from\ baseline = 100 \times \frac{Baseline\ PASI - Observed\ PASI}{Baseline\ PASI}$	Missing if baseline or observed value is missing

Measure	Description	Variable	Derivation / Comment	Imputation Approach if with Missing Components
	The various body regions are weighted to reflect their respective proportion of body surface area.		If a patient has experienced an improvement, this measure will be positive. If a patient has experienced a worsening in the condition, this measure will be negative.	
		PASI 75	A clinically meaningful response; at least a 75% improvement in PASI score from baseline	Missing if baseline or observed value is missing
		PASI 90 (Primary)	Higher level of clearance; at least a 90% improvement in PASI score from baseline	Missing if baseline or observed value is missing
		PASI 100	Complete resolution of plaque Ps; a 100% improvement in PASI score from baseline	Missing if baseline or observed value is missing
sPGA	Static Physician Global Assessment (sPGA): the physician's global assessment of the patient's psoriasis (Ps) lesions at a given time point (European Medicines Agency [EMA] 2004). Plaques are assessed for induration, erythema, and scaling, and an overall rating of psoriasis severity is given using the anchors of clear (0), minimal (1), mild (2), moderate (3), severe (4), or very severe (5).	sPGA score	Range from 0 to 5: clear (0), minimal (1), mild (2), moderate (3), severe (4), or very severe (5).	Single item, missing if missing
		sPGA (0,1)	An sPGA assessed as either 0 or 1, which represents a clinically meaningful response of minimal plaque severity or complete resolution of plaque Ps.	Missing if sPGA is missing
		sPGA (0)	An sPGA assessed as 0, which represents a clinically important endpoint indicating complete resolution of plaque Ps.	Missing if sPGA is missing
BSA	Percentage of Body Surface Area (BSA): The investigator will evaluate the percentage involvement of psoriasis on each patient's BSA on a continuous scale from 0% (no involvement) to 100% (full involvement), in which 1% corresponds to the size of the patient's hand (including the palm, fingers, and thumb).	BSA	Collected as a single scale as part of PASI electronic case report form eCOA. Range from 0% to 100%.	Single item, missing if missing
		BSA change from baseline	Calculated as: observed BSA – baseline BSA	Missing if baseline or observed value is missing

Measure	Description	Variable	Derivation / Comment	Imputation Approach if with Missing Components
PSSI	Psoriasis Scalp Severity Index (PSSI): will be used if the patient has scalp psoriasis at baseline. The scalp will be assessed for erythema (redness), induration (hardness), and desquamation (shedding of skin) and percentage of area affected as follows: Erythema, Induration and Desquamation: 0 = Absent 1 = Slight 2 = Moderate 3 = Severe 4 = Severest Possible Percent of Scalp Involved: 0 = none 1 = <10% 2 = 10 – 29% 3 = 30 – 49% 4 = 50 – 69% 5 = 70 – 89% 6 = 90 – 100%	PSSI score	The PSSI score is a composite score derived from the sum of the scores for erythema, induration and desquamation multiplied by the score for the extent of scalp area involved (percent of scalp involved). The range is 0 to 72.	If any individual score is missing, the PSSI score will not be calculated, hence missing.
		PSSI improvement from baseline and percent change from baseline (for subjects with baseline scalp psoriasis involvement only)	Calculated as: observed PSSI – baseline PSSI	Missing if baseline or observed value is missing
		PSSI score =0	A PSSI response is defined as a PSSI score of 0, which is also referred to as scalp clearance.	Missing if PSSI score is missing
DLQI	Dermatology Life Quality Index (DLQI): is a validated, dermatology-specific, patient-reported measure that evaluates patient’s health-related quality of life. This questionnaire has 10 items that are grouped in 6 domains, including symptoms and feelings, daily activities, leisure, work and school, personal relationships, and treatment. The recall period of this scale is over the “last week”. Response categories and corresponding scores are:	DLQI symptoms and feelings domain	Sum of responses of questions #1 and #2: #1. How itchy, sore, painful or stinging has your skin been? #2. How embarrassed or self-conscious have you been because of your skin?	If 1 question in a domain is missing, that domain is missing.
		DLQI daily activities domain	Sum of responses of questions #3 and #4: #3. How much has your skin interfered with you going shopping or looking after your home or garden? #4. How much has your skin influenced the clothes you wear?	If 1 question in a domain is missing, that domain is missing.

Measure	Description	Variable	Derivation / Comment	Imputation Approach if with Missing Components
	Very much = 3 A lot = 2 A little = 1 Not at all = 0 Not relevant = 0	DLQI leisure domain	Sum of responses of questions #5 and #6: #5. How much has your skin affected any social or leisure activities? #6. How much has your skin make it difficult for you to do any sport?	If 1 question in a domain is missing, that domain is missing.
		DLQI work and school domain	Sum of responses of questions question #7A and #7B: #7A. Has your skin prevented you from working or studying? #7B. If No: how much has your skin been a problem at work or studying?	If the answer to question #7A is missing, this domain is missing. If #7A is No, and #7B is missing, this domain is missing.
		DLQI personal relationships domain	Sum of responses of questions #8 and #9: #8. How much has your skin created problems with your partner or any of your close friends or relatives? #9. How much has your skin caused any sexual difficulties?	If 1 question in a domain is missing, that domain is missing.
		DLQI treatment domain	Response of question #10: #10. How much of a problem has the treatment for your skin been, for example by making your home messy, or by taking up time?	If 1 question in a domain is missing, that domain is missing.
		DLQI total score	A DLQI total score is calculated by summing all 10 question responses, and has a range of 0 to 30 (less to more impairment) (Finlay and Khan 1994; Basra et al. 2008).	If 2 or more questions are missing, the total score is missing. Note: #7B could be a valid missing while #7A is not “No.” That is, #7 should be considered as 1 question.
		DLQI (0,1)	A DLQI (0,1) response is defined as a post-baseline DLQI total score of 0 or 1. A DLQI total score of 0	Missing if DLQI total score is missing

Measure	Description	Variable	Derivation / Comment	Imputation Approach if with Missing Components
			to 1 is considered as having no effect on a patient’s HRQoL (Khilji et al. 2002; Hongbo et al. 2005).	
		DLQI (0)	A DLQI (0) response is defined as a postbaseline DLQI total score of 0.	Missing if DLQI total score is missing
		DLQI total score ≥ 5	A DLQI total score ≥ 5 response is defined as a postbaseline DLQI total score ≥ 5 .	Missing if DLQI total score is missing
		DLQI total score and domain scores change from baseline	Calculated as: observed DLQI (total score or domain scores) – baseline DLQI (total score or domain scores)	Missing if baseline or observed value is missing
SF-36	
The SF-36 is a 36-item, patient-completed measure designed to be a short, multipurpose assessment of health (The SF Community – SF-36 Health Survey Update). The summary scores range from 0 to 100, with higher scores indicating better levels of function and/or better health. Items are answered on Likert scales of varying lengths. The SF-36 comprises 8 domain scores and 2 overarching component scores. The SF-36 acute version will be used, which has a 1 week recall period.
 
Minimal Clinically Important Difference (MCID) cut-offs were determined in Strand et al. 2013.
	SF-36 Domain scores: Physical functioning, Role-physical, Role-emotional, bodily pain, vitality, social functioning, mental health, general health	
Per copyright owner, the Quality Metric Health Outcomes™ Scoring Software 4.5 will be used to derive SF-36 domain and component scores.
 
After data quality-controls, the SF-36 software will re-calibrate the item-level responses for calculation of the domain and component scores. These raw scores will be transformed into the domain scores (t-scores) using the 1-week recall period. No missing-imputation method will be used. Both, raw and domain scores without missing-data imputation will be recorded in the SDTM dataset, however only the domain scores will be used for analyses specified in this SAP.
	Missing data handling offered by SF-36 software will be used.
		SF-36 Component Scores: PCS and MCS		

Measure	Description	Variable	Derivation / Comment	Imputation Approach if with Missing Components
		SF-36 change from baseline for domain and component scores	Calculated as: observed SF-36 domain score – baseline SF-36 domain score	Missing if baseline or observed value is missing
		SF-36 Physical Component response (PCS)	PCS component score (change from baseline) ≥ 2.5	Missing if baseline or observed value is missing
		SF-36 Mental Component response (MCS)	MCS component score (change from baseline) ≥ 2.5	Missing if baseline or observed value is missing
PSS	
The Psoriasis Symptoms Scale (PSS) is a patient-administered assessment of 8 symptoms: itch, pain, discomfort, stinging, burning, redness, scaling, and cracking. Respondents are asked to answer the questions based on their psoriasis symptoms.
 
The overall severity for each individual symptom from patient’s psoriasis is indicated by selecting the number from an NRS of 0 to 10 that best describes the worst level of each symptom in the area in the past 24 hours, where 0 (= no severity) and 10 (worst imaginable severity).
 
The symptom severity scores, ranging from 0 to 10, are the values of the selected numbers indicated by the patient on the instrument’s horizontal scale. Each of the 8 individual items will receive a score of 0 to 10 and will be reported as item scores for itch, pain, discomfort,
	PSS total score	
The PSS total score will be calculated by summing the individual item scores as follows: PSS = itch NRS + pain NRS + discomfort NRS + stinging NRS + burning NRS + redness NRS + scaling NRS + cracking NRS
	If any item score are missing, the PSS total score is missing
		PSS change from baseline	
Change from baseline = Observed PSS Total Score – Baseline PSS Total Score A negative change indicates improvement and a positive change indicates deterioration of the condition.
	Missing if either observed or baseline PSS total score is missing
		PSS item scores	The PSS score for each item as reported in daily diaries from visit1 up to visit 7, then on the tablet device at visits 7, 11, 16 and 28 (see Appendix 2).	Missing if the PSS score for the item is missing
		Change from baseline for item scores	
Change from baseline = Observed PSS Item Score – Baseline PSS Item Score A negative change indicates improvement and a positive change indicates deterioration of the condition.
	Missing if either observed or baseline item PSS score is missing

Measure	Description	Variable	Derivation / Comment	Imputation Approach if with Missing Components
	stinging, burning, redness, scaling, and cracking. In addition, a total score ranging from 0 (no psoriasis symptoms) to 80 (worst imaginable psoriasis symptoms) will be reported.			
PatGA	The Patient’s Global Assessment of Psoriasis (PatGA) is a patient reported, single item scale on which subjects are asked to rank, by selecting a number on a 0-to-5 NRS, the severity of their psoriasis “today” from 0 (clear), no psoriasis, to 5 (severe).	Change from baseline	Change from baseline = Observed Item PatGA score – Baseline Item PatGA score	Missing if baseline or observed value is missing

Abbreviations: BSA = body surface area; DLQI = Global Assessment Dermatology Life Quality Index; EMA = European Medicines Agency; HRQoL = health-related quality of life; MCS = Mental Component Score; MCID = Minimal Clinically Important Difference; NRS = Numeric Rating Scales; PASI = Psoriasis Area and Severity Index; PatGA = Patients Global Assessment of Psoriasis; PCS = Physical Component Score; Ps = psoriasis; PSS = Psoriasis Symptoms Scale; PSSI = Psoriasis Scalp Severity Index; sPGA = Static Physician Global Assessment

Table 6.3. Description of Efficacy/Health Outcomes Analyses

Measure	Variable	Analysis Method (Sections 6.1.3)	Population (Section 6.1.1)	Time Point
PASI	PASI 90 (Primary)	Logistic regression analysis with NRI	ITT Population	Week 16: All pairwise comparisons against placebo (primary analysis), and linear trend tests (supportive analysis)
	PASI 75, PASI 90, PASI 100	Logistic regression analysis with NRI	ITT Population	All pairwise comparisons against placebo at all postbaseline visits in Induction Period
		Summary statistics with NRI	Maintenance Period Efficacy Population	All visits in Maintenance Period
		Summary statistics (As observed) or individual trajectory line plot if total number of subjects is too small	Rescue Period Efficacy Population	All visits in Rescue Period
	PASI <5; PASI <3; PASI <1	Logistic regression analysis with NRI	ITT Population	All pairwise comparisons against placebo at all postbaseline visits in Induction Period
	PASI change from baseline, percent improvement from baseline	MMRM; mBOCF ANCOVA	ITT Population	All pairwise comparisons against placebo at all postbaseline visits in Induction Period
		MMRM	Maintenance Period Efficacy Population	All visits in Maintenance Period
		Summary statistics (As observed) or individual trajectory line plot if total number of subjects is too small	Rescue Period Efficacy Population	All visits in Rescue Period
	Time to first loss of response (PASI 90, PASI 100) for PRN subjects	KM product limit curve; time to loss of response	Maintenance Period Efficacy Population	Maintenance Period

Measure	Variable	Analysis Method (Sections 6.1.3)	Population (Section 6.1.1)	Time Point
	Time to recapture of response (PASI 90, PASI 100) after first loss of response for PRN subjects	KM product limit curve; time to response recapture after first loss of response	Maintenance Period Efficacy Population	Maintenance Period
	Time to recapture of response (PASI 50, PASI 90) after loss of response for rescued subjects	KM product limit curve; time to response recapture after first loss of response	Rescue Period Efficacy Population	Rescue Period
sPGA	sPGA (0,1); sPGA (0)	Logistic regression analysis with NRI	ITT Population	All pairwise comparisons against placebo at all postbaseline visits in Induction Period
		Summary statistics with NRI	Maintenance Period Efficacy Population	All visits in Maintenance Period
		Summary statistics (As observed) or individual trajectory line plot if total number of subjects is too small	Rescue Period Efficacy Population	All visits in Rescue Period
BSA	BSA change from baseline	MMRM; mBOCF ANCOVA	ITT Population	All pairwise comparisons against placebo at all postbaseline visits in Induction Period
		MMRM	Maintenance Period Efficacy Population	All visits in Maintenance Period
PSSI	PSSI percent improvement from baseline (for subjects with scalp psoriasis involvement only); PSSI score (for all subjects)	MMRM; mBOCF ANCOVA	ITT Population	All pairwise comparisons against placebo at all postbaseline visits in Induction Period
		MMRM	Maintenance Period Efficacy Population	All visits in Maintenance Period
	PSSI score = 0 (for all subjects)	Logistic regression analysis with NRI	ITT Population	All pairwise comparisons against placebo at all postbaseline visits in Induction Period
	Summary statistics with NRI	Maintenance Period Efficacy Population	All visits in Maintenance Period	

Measure	Variable	Analysis Method (Sections 6.1.3)	Population (Section 6.1.1)	Time Point
DLQI	DLQI (0,1), DLQI (0)	Logistic regression analysis with NRI	ITT Population	All pairwise comparisons against placebo at all postbaseline visits in Induction Period
		Summary statistics with NRI	Maintenance Period Efficacy Population	All visits in Maintenance Period
	DLQI total score and domain scores change from baseline	MMRM;	ITT Population	All pairwise comparisons against placebo at all postbaseline visits in Induction Period
		ANCOVA	Maintenance Period Efficacy Population	All visits in Maintenance Period
SF-36	SF-36 change from baseline for Domain Scores and Component Scores	ANCOVA	ITT Population	All pairwise comparisons against placebo at all postbaseline visits in Induction Period
		ANCOVA	Maintenance Period Efficacy Population	All visits in Maintenance Period
	SF-36 Physical Component (PCS) and Mental Component (MCS) Response	Logistic regression analysis with NRI	ITT Population	All pairwise comparisons against placebo at all postbaseline visits in Induction Period
		Summary statistics with NRI	Maintenance Period Efficacy Population	All visits in Maintenance Period
PatGA	Change from baseline	MMRM	ITT Population	All pairwise comparisons against placebo at all postbaseline visits in Induction Period
		ANCOVA	Maintenance Period Efficacy Population	All visits in Maintenance Period
PSS	PSS total score and item scores change from baseline	MMRM; mBOCF ANCOVA	ITT Population	All pairwise comparisons against placebo at all postbaseline visits in Induction Period
		ANCOVA	Maintenance Period Efficacy Population	All visits in Maintenance Period

Measure	Variable	Analysis Method (Sections 6.1.3)	Population (Section 6.1.1)	Time Point
		Summary statistics (As observed) or individual trajectory line plot if total number of subjects is too small	Rescue Period Efficacy Population	All visits in Rescue Period

Abbreviations: ANCOVA = analysis of covariance; BSA = body surface area; DLQI = Global Assessment Dermatology Life Quality Index; ITT = intent-to-treat; KM = Kaplan-Meier; mBOCF = modified baseline observation carried forward; MCS = Mental Component Score; MMRM = mixed model repeating measures; NRI = non-responder imputation; PASI = Psoriasis Area and Severity Index; PatGA = Patients Global Assessment of Psoriasis; PCS = Physical Component Score; PSS = Psoriasis Symptoms Scale; PSSI = Psoriasis Scalp Severity Index; sPGA = Static Physician Global Assessment.

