### **9.1.3. Additional Efficacy Assessments/Disease Activity Measures**

Percent BSA will be evaluated as the percent involvement of psoriasis on each subject's BSA on a continuous scale from 0% (no involvement) to 100% (full involvement), where 1% corresponds to the size of the subject's hand (including the palm, fingers, and thumb) (National Psoriasis Foundation 2009).

Psoriasis Scalp Severity Index (PSSI) measures the affected scalp area and the severity of clinical symptoms. If the subject has scalp psoriasis at any time during the study, the PSSI will be used for all remaining visits. The PSSI is a composite score derived from the sum of scores for erythema, induration, and desquamation multiplied by a score for the extent of scalp area involved (range 0 to 72). Higher scores indicate worse severity (Thaci et al. 2015).

Clinical whole body photographs will be collected at the times shown in the Schedule of Activities (Section 2) for patients who have given their consent to have photographs taken. Detailed instructions for obtaining clinical photographs will be provided in a study manual. Documentation of the clinical improvement will be permitted through sequential whole body photography before and after study treatment.

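### The SAP's only PSSI change formula is a difference in points, so it has the wrong sign and scale for the percent improvement that is to be analysed

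*SAP*

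**What the plan says.** SAP Section 6.9 puts derivations in Table 6.2 and analyses in Table 6.3.

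- **Table 6.2, PSSI.** The score is the sum of three severity items multiplied by an area grade: "The range is 0 to 72". One row then carries two derived variables, "PSSI improvement from baseline and percent change from baseline (for subjects with baseline scalp psoriasis involvement only"), and its only derivation is "Calculated as: observed PSSI – baseline PSSI".
- **Table 6.3, PSSI.** The analysed variable has a third name: "PSSI percent improvement from baseline (for subjects with scalp psoriasis involvement only"). The induction method is "MMRM; mBOCF ANCOVA" in the ITT population. In the maintenance period it is MMRM.
- **Protocol Section 9.1.3.** This fixes the direction of the scale: "Higher scores indicate worse severity".
- **Table 6.2, PASI.** Here the two ideas have separate rows. Change is observed minus baseline. The row for "PASI percent improvement from baseline" uses 100 × (baseline − observed) / baseline, and the sign rule is explicit: "If a patient has experienced an improvement, this measure will be positive".

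**The concern.** A derivation table should tell a programmer exactly what to compute. The PSSI row attaches a plain difference to two labels and fits neither. Under the improvement label the sign is reversed. Under the percent change label the sign is acceptable, but the division by baseline and the factor of 100 are missing. The variable in Table 6.3, percent improvement, has no derivation under its own name, and the only candidate fails it on both counts.

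Followed as written, the SAP would report an absolute change in points, with worsening shown as a positive value, under a heading that promises percent improvement. Programmers could also reasonably build three different datasets from the same text: points, percent change or percent improvement.

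**Working it through.** No sample size, power or error rate enters this point. The only stated figure to reproduce is the score range. Each of the three severity items runs from 0 to 4 and the area grade from 0 to 6, so the maximum is (4 + 4 + 4) × 6 = 72 and the minimum is 0. This agrees with the SAP.

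**Formulas compared** (B = baseline PSSI, O = observed PSSI):

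- (a) Table 6.2 as written: O − B
- (b) Percent change: 100 × (O − B) / B
- (c) Percent improvement, in the form the SAP uses for PASI: 100 × (B − O) / B

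The baseline and observed pairs are illustrative assumptions. The documents give no PSSI data.

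| B to O | (a) as written, points | (b) percent change | (c) percent improvement |
|---|---|---|---|
| 4 to 1 | -3 | -75% | +75% |
| 24 to 6 | -18 | -75% | +75% |
| 72 to 18 | -54 | -75% | +75% |
| 24 to 30 | +6 | +25% | -25% |
| 10 to 0 | -10 | -100% | +100% |
| 40 to 20 | -20 | -50% | +50% |

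**Sign.** A patient who goes from 24 to 6 is better and gets -18. A patient who goes from 24 to 30 is worse and gets +6. This is the opposite of the convention the SAP states for PASI.

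**Scale.** The first three patients have the same 75% improvement, yet (a) gives -3, -18 and -54. The value follows the baseline score as much as the response.

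**Ordering.** Full clearance from 10 gives -10, and a half response from 40 gives -20. The lesser percent improvement looks like the larger effect. Reversing the sign does not repair this, because the two quantities are different outcomes.

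**What the model would estimate.** SAP Section 6.1.3 puts the baseline value in both the MMRM and the ANCOVA. Subtracting B from every observed score only lowers the baseline coefficient by 1 and leaves the treatment difference unchanged. In the same subjects and with the same imputation, formula (a) therefore gives the same treatment contrast as the PSSI score itself, which Table 6.3 already lists for analysis in all subjects. The percent analysis would then differ only in its subject restriction.

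**Denominator.** Formula (c) is undefined at B = 0. Table 6.2 limits the row to subjects with scalp involvement at baseline, but Table 6.3 drops the word baseline from its restriction. Protocol Section 9.1.3 starts PSSI whenever scalp psoriasis appears, and SAP Section 6.6 includes subjects who develop it later. The set of subjects with a usable denominator therefore needs to be stated.

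**The case against.** The strongest reply is that this is a drafting slip with an obvious repair. Table 6.3 gives no formula, so the planned analysis goes wrong only if someone applies a points difference to a variable called percent. The PASI rows supply both the percent formula and the sign rule, and observed minus baseline is the SAP's usual form for change. Most likely the change formula was carried into a merged row and the percent form was left out. A sign reversal alone would not alter p-values or the size of treatment differences, and a percent result reported in points would be easy to notice. PSSI is exploratory (SAP Section 6.9.3), and the PSSI score in points and scalp clearance are analysed separately.

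Most of this stands, and it sets the weight of the point. It is right that the error takes effect only under literal programming, and that the formula is partly right for each Table 6.2 label taken alone: the size in points for improvement, the direction for percent change. It does not remove the error. The stated rule is still wrong for the variable to be analysed, the missing division changes the outcome and can change the ordering of patients, and the analysed name has no derivation of its own. SAP Section 6.3.3 also names PSSI among the key continuous endpoints for the mBOCF sensitivity analysis, so the derivation will be used.

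**Conclusion.** The point holds as a minor error. Applied literally, Table 6.2 gives a quantity with the wrong sign and the wrong scale for the PSSI percent improvement in Table 6.3, for example -18 in place of +75% for a fall from 24 to 6. The effect on real results cannot be sized from the documents because they contain no PSSI data.

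The conclusion rests on the protocol's direction for the scale and on the absence of any other PSSI percent derivation in the protocol or SAP. It also takes the SAP's own PASI formula as the standard for percent improvement. The primary PASI 90 analysis, the secondary endpoints and the PSSI of 0 response are unaffected.

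**What to change.** In SAP Table 6.2, split the merged PSSI row into two:

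1. PSSI change from baseline = observed PSSI − baseline PSSI.
2. PSSI percent improvement from baseline = 100 × (baseline PSSI − observed PSSI) / baseline PSSI, for subjects with baseline PSSI above 0, with positive values meaning improvement.

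In Table 6.3, use the same variable name and the same baseline restriction, so that the analysed variable points to row 2.

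The cost is a short text edit in two tables and a check that the analysis dataset program uses row 2. Design, data collection and sample size do not change. Because no principal feature of the protocol is affected, Protocol Section 10.3.1 would let the correction be described in the clinical study report without an amendment.
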